15.2 Serious Adverse Events

An SAE is defined as any untoward medical occurrence that at any dose:

- Results in death;
- Is life-threatening;
- Requires hospitalization or prolongation in existing hospitalization;
- Results in persistent or significant disability or incapacity;
- Is a congenital anomaly or birth defect;
- Is other medically important event.

15.3 Adverse Events Listings

All AEs, SAEs, AEs leading to treatment period discontinuation, and AEs with outcome of death, including the applied coded terms, will be presented in subject listings. Each AE listing will include onset and resolution date, coded term, SOC, PT, relatedness, seriousness, severity, outcome and action taken. Treatment-emergent events will be flagged in these listings.

15.4 Physical Examination

The subject will undergo an evaluation of all major body systems (abdomen, cardiovascular, chest and lungs, ENT [ears, nose and throat], extremities, general appearance, genitourinary, head and neck, lymphatic, musculoskeletal, neuromuscular, skin). Body systems will be classified as Normal or Abnormal, and if abnormal, details will be provided. Physical examinations will be performed at the Screening Visit, at Visits -3, -2, -1, TP1-EXT, End of Study-TP1, 1, 3, 5, 7, 9, 11, 13, at all subsequent quarterly Study Visits, and at the Safety Follow-Up TP2 Visit. A subject listing of the physical examination results at Treatment Period and Visit will be produced.

15.5 Performance Status

A subject will be assigned a GOG Performance Status at the Screening Visit and at Visits -3, -2, -1, TP1-EXT, End of Study-TP1, 1, 3, 5, 7, 9, 11, 13, all subsequent quarterly Study Visits, and at the Safety Follow-Up TP2 Visit, in accordance with the following table:

Gynecologic Oncology Group (GOG) Status Scale	
GOG Score	Descriptions
0	Fully active, unrestricted activities of daily living.
1	Ambulatory, but restricted in strenuous activity.
2	Ambulatory, and capable of self care. Unable to work. Out of bed for greater than 50% of waking hours.
3	Limited self care, or confined to bed or chair 50% of waking hours. Needs special assistance.
4	Completely disabled, and no self care.
5	Dead.

Performance Status including change from Treatment Period baseline will be provided in a subject listing.

15.6 Vital Signs

The subject will undergo an assessment of vital signs (diastolic and systolic blood pressure, heart rate and body temperature) after 5 minutes in a supine position at the Screening Visit, at all Study Visits, at the End of Study-TP1 Visit, and at the Safety Follow-Up TP2 Visit.

A subject listing of the vital signs results will be provided.

15.7 Height, Weight and Body Mass Index

Height will be measured once at screening. Weight is measured and Body Mass Index (BMI) calculated at Screening, Visits -3, -2, -1, TP1-EXT, End of Study-TP1, 1, 3, 5, 7, 9, 11, 13, all subsequent quarterly Study Visits, and at the Safety Follow-Up TP2 Visit. BMI will be calculated in accordance with the formula:

$$\text{BMI (kg/m}^2\text{)} = \text{Weight (kg)} / [\text{Height (cm)}^2 \times 10000]$$

BMI, height, and weight will be provided in a listing.

15.8 Electrocardiogram (ECG)

A 12-lead ECG will be performed to evaluate potential study drug-induced QT prolongation potential at the Screening Visit, at Study Visit -3 prior to the first dose of megestrol acetate, at all remaining Study Visits (prior to administration of megestrol acetate whenever possible), and at the End of Study-TP1 Visit and the Safety Follow-Up TP2 Visit. At Visits 1 and 3 during Treatment Period 2, ECG will be performed 5 times: before administration of both SC and MA, and at 15, 60, 120, and 360 (\pm 5) minutes after administration of SC. ECGs at all other visits will be performed only once, prior to administration of both SC and MA (in Treatment Period 1 prior to MA dosing). For all ECGs performed after the first dose of SC, any clinically significant changes compared with the ECG recorded at the Screening Visit must be

reported as an AE. All ECG intervals (PR, QRS, QT, QTcB [QT interval corrected for heart rate using Bazett's formula], QTcF [QT interval corrected for heart rate using Fridericia's formula] and RR) will be reported in the eCRF. ECG intervals (PR, QRS, QT, QTcB, QTcB, QTcF and RR), plus Overall results of the ECG (normal; abnormal, not clinically significant; and abnormal, clinically significant) will be presented as listings.

Categorical analysis of QTcB and QTcF relative to the following clinically significant cut-points will be presented in a summary table

- $450 < QTcB/F \leq 480$ msec
- $480 < QTcB/F \leq 500$ msec
- $QTcB/F > 500$ msec
- QTcB/F Increase of > 30 and ≤ 60 msec from Baseline
- QTcB/F Increase of > 60 msec from Baseline

(For Visit -2, Visit -1, TP1-EXT, and End of Study-TP1 baseline is with respect to Treatment Period 1.
For all other visits, baseline is with respect to Treatment Period 2.)

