1.3. Summary of Key Safety Information for Study Drug

Acute toxicity of Sodium Cridanimod has been studied in mice, rats, hamsters and rabbits, with intramuscular administration not shown to cause deaths in any of these species. Repeated dose toxicity studies have been performed in rats, rabbits and dogs. These studies have not identified any target organ toxicity at doses as high as 31.3 mg/kg i.m. Sodium Cridanimod is known to be eliminated mostly by the kidney with a half-life of approximately 0.6 hours.

More than 750 subjects have been exposed to Sodium Cridanimod in clinical studies. The regimen of administration of Sodium Cridanimod was similar across clinical studies: study drug was administered at the dose of either 250 or 500 mg either two or three times a week intramuscularly, in some cases for as long as 2 years. All of these trials have demonstrated that Sodium Cridanimod is well tolerated, with mild to moderate adverse events (AEs) and no subjects ever permanently discontinuing study drug due to an AE related to administration of Sodium Cridanimod. The most frequently reported AE across the studies was moderate intensity pain at the site of injection. There have been no deaths associated with the administration of Sodium Cridanimod. Table 6 below summarizes the related, AEs observed in all subjects who were treated with Sodium Cridanimod in all studies to date.

Table 6. Adverse Events with causal relationship to Sodium Cridanimod

Adverse Event	Investigator Causality Assessment	AE Frequency per Study	Total Subjects with reported AE to date*	Frequency of AE based on total Subjects treated*
Burning pain at the injection site	Related	729 of 751 (97%)	730	96.18 %
Relative eosinophilia	Probably related	6 of 50 (12%)	6	0.79 %
Burning Lips	Probably related	1 of 8 (13%)	1	0.13 %
Fatigue and tired all the time	Probably related	1 of 8 (13%)	1	0.13 %
Hyperemia of the face	Probably related	1 of 8 (13%)	1	0.13 %
Pharyngalgia	Probably related	1 of 8 (13%)	1	0.13 %
Sleepiness	Probably related	1 of 8 (13%)	1	0.13 %
Headache	Possibly related	4 of 12 (33%), 1 of 8 (13%)	5	0.66 %
Sore throat	Possibly related	4 of 12 (33%), 1 of 8 (13%)	5	0.66 %
Weakness	Possibly related	2 of 6 (33%), 1 of 8 (13%)	3	0.40 %
Dizziness	Possibly related	2 of 6 (33%)	2	0.26 %
Sleepiness	Possibly related	2 of 6 (33%)	2	0.26 %

*Data from 759 subjects in clinical trials through 1Sep2017

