7.5.5. Electrocardiogram

Results of ECG (“normal”, “with clinically non-significant deviations from normal”, and “with clinically significant deviations from normal”) will be presented as listings and as summaries for each measurement point.

ECG intervals (QT and QT intervals adjusted by an appropriate correction [QTcB and QTcF; Bazett and Fridericia], PR, QRS, and RR) will be summarized at each scheduled timepoint, along with mean change from baseline to each post treatment timepoint.

ECG intervals (QTcB and QTcF; Bazett and Fridericia) recorded at Visits 1 and 3 will be presented both as analyses of central tendency and categorical analyses.

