D - For the subjects who consented to participate in the PK sub-study, blood samples are taken before administration of Sodium Cridanimod and megestrol acetate as well as 15 min, 30 min, 45 min, 60 min, 90 min, 2, 3, 4 and 6 hours (all times +/- 2 minutes) after administration at Visit 1. Blood samples are also taken on Days 3, 7, 10, 56 (Visit 3) and 84 (Visit 4), before Sodium Cridanimod and megestrol acetate administration.															
E - ECG will be performed 5 times at Visits 1 and 3: before Sodium Cridanimod administration, 15, 60, 120 and 360 (\pm 5) minutes after administration. At all other visits, ECG is only performed before administration. Exception: ECG performed at Safety Follow-up Visit.															
F - Subjects with disease control (non-PD) after one year of treatment in Period 2 (Visit 13) will continue treatment and will switch to study visits every 12 weeks, until discontinuation of treatment.															
G - Safety Follow-up Visit occurs four weeks following the discontinuation of treatment.															
H - At the visit where treatment is discontinued, study drug will not be dispensed, and a new patient diary will not be issued. The remaining drug will be returned and the final patient diary will be collected.															
I - After subjects discontinue treatment and undergo the Safety Follow-up Visit, they will be followed for overall survival for an additional 12 months (from the date of treatment discontinuation) by phone call or other personal contact.															
J - D = Dispense, R = Return, I = Issue, C = Collect															

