9.3 Definition of Baseline

Baseline is defined as the last measurement prior to the first dose of study medication. In Treatment Period 1 this will be the last measurement prior to the first dispensing of MA (Visit -3). In Treatment Period 2 this will be the last measurement prior to the first in-clinic administration of MA and SC (Visit 1, Day 0-TP2). For subjects treated in both Treatment Period 1 and Treatment Period 2, baseline resets at the start of Treatment Period 2. Change from baseline will be calculated as the value at the time point of interest minus the baseline value.

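### At Visit 3 the QTc change categories use the Visit 1 baseline and so mix any acute effect with about 8 weeks of drift and exposure; the planned central-tendency analysis at Visits 1 and 3 is also missing

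*SAP*

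**What the plan says.** SAP 15.8 schedules five ECGs at each of Visits 1 and 3: one before dosing, then at 15, 60, 120 and 360 minutes after Sodium Cridanimod. On analysis it says: "Categorical analysis of QTcB and QTcF relative to the following clinically significant cut-points will be presented in a summary table". Three categories are absolute (>450 to 480, >480 to 500 and >500 msec). Two are changes from baseline (>30 to 60 and >60 msec).

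For the visits of Treatment Period 1 after dosing starts, the change is taken from that period's baseline. The rule then continues: "For all other visits, baseline is with respect to Treatment Period 2". SAP 9.3 defines the latter: "In Treatment Period 2 this will be the last measurement prior to the first in-clinic administration of MA and SC", that is, Visit 1, Day 0. It adds: "For subjects treated in both Treatment Period 1 and Treatment Period 2, baseline resets at the start of Treatment Period 2".

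Protocol 7.5.5 planned mean change from baseline at each post-treatment time point for the ECG intervals. It also says that QTcB and QTcF "recorded at Visits 1 and 3 will be presented both as analyses of central tendency and categorical analyses". SAP 15.8 and the title of Table 14.3.3.7 provide for categories only. SAP section 20 says in general terms that, because of early closure, everything except one QTc category table is reduced to listings. It does not name the dropped central-tendency analysis.

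**The concern.** The serial ECGs at Visits 1 and 3 are there to look for drug-induced QT prolongation after an injection. For that question the natural reference at Visit 3 is the pre-dose ECG of the same day. Under the SAP's rule, a Visit 3 subject can enter or miss a change category because QTc moved over 8 weeks, whatever happened in the hours after the injection.

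The mixture also differs between subgroups. PrR-negative subjects enter Treatment Period 2 directly, and prior progestin therapy is an exclusion criterion (Protocol 3.5). Their Visit 1 baseline is therefore free of megestrol, while Visit 3 follows 8 weeks of it. Subjects arriving from Treatment Period 1 have already taken megestrol for at least 4 weeks at their baseline. The same count above 30 msec does not mean the same thing in the two groups.

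Threshold counts also respond weakly to a moderate shift of the whole distribution. Mean change by time point would show such a shift, and that is the summary left out.

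**Working it through.** The plan gives no figure to reproduce here. The check traces the baseline rule and then illustrates its size under stated assumptions.

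**Baseline by visit (SAP 9.3 and 15.8)**

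- Visit 1, post-dose: the baseline is the pre-dose ECG scheduled for the same visit. Nothing to correct.
- Visit 3, post-dose: the baseline is still the Visit 1 pre-dose ECG. Week 8 is 8 × 7 = 56 days later. With ±3 days on each visit, the gap is 56 − 6 = 50 to 56 + 6 = 62 days.
- Absolute categories: no baseline enters.

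**Is the Visit 3 pre-dose ECG usable as a reference?** Protocol 1.3 gives a "half-life of approximately 0.6 hours". Scheduled injections are 72 or 96 hours apart, which is 72/0.6 = 120 or 96/0.6 = 160 half-lives. The make-up rule allows a late dose up to one day before the next, and 24/0.6 = 40 half-lives still remain. Parent drug should be negligible. Two cautions apply: the half-life is quoted without species or route, and clearance of drug does not prove absence of a lasting effect.

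**Illustration A: no drug effect, no drift**

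Assumed, not in the documents: for a single QTcF, a between-visit SD of 12 msec and a within-day SD of 8 msec; 10 subjects at Visit 3.

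- SD of change, Visit 1 baseline: √(2 × (12² + 8²)) = √416 = 20.4 msec
- SD of change, same-day baseline: √(2 × 8²) = √128 = 11.3 msec
- P(change > 30): P(Z > 30/20.4) = 7.1%, against P(Z > 30/11.3) = 0.4%
- P(change > 60), Visit 1 baseline: P(Z > 60/20.4) = 0.16%
- Expected false entries above 30 msec over 10 × 4 = 40 Visit 3 post-dose ECGs: 40 × 0.071 = 2.8, against 40 × 0.004 = 0.16
- 95% CI half-width for mean change, n = 10: 2.262 × 20.4/√10 = 14.6 msec, against 2.262 × 11.3/√10 = 8.1 msec
- The same with n = 25, the total enrolled and so an upper limit: 2.064 × 20.4/5 = 8.4 msec, against 2.064 × 11.3/5 = 4.7 msec

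With between-visit SD from 10 to 15 msec, the Visit 1-baseline SD of change is √(2 × (100 + 64)) = 18.1 to √(2 × (225 + 64)) = 24.0 msec, and the false rate is 5% to 11%. With between-visit SD of zero, both baselines give 11.3 msec and the difference is gone.

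**Illustration B: drift and an acute effect**

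Here the assumed SDs are those of the change itself: same-day 10 to 12 msec, 8-week 10 to 18 msec. The formula is P(Z > (30 − effect − drift)/SD), with drift only in the 8-week comparison.

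| Acute effect | Drift | Same-day baseline | Visit 1 baseline |
|---|---|---|---|
| 0 | 0 | 0.13% to 0.62% | 0.13% to 4.8% |
| 0 | +10 | 0.13% to 0.62% | 2.3% to 13% |
| 20 | −15 to +15 | 16% to 20% | 0.6% to 69% |

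With no drift and both SDs at 10 msec, a 20 msec effect gives 15.9% under either baseline.

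**Sensitivity of the categories.** Even with a same-day baseline, a true mean rise of 20 msec leaves 80% to 84% of ECGs outside both change categories. An observed mean rise of 20 msec with the half-width of 8.1 msec from Illustration A would have a 95% CI of about 12 to 28 msec.

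**The case against.** The strongest reply is that this is an abbreviated report of a study closed at 25 of 72 planned subjects. SAP section 1 says its methods supersede the protocol's, section 2 says none of the objectives will be analysed, and section 20 announces one QTc category table and listings. That stands as an explanation and as general disclosure. It does not make the remaining table as informative as it could cheaply be.

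A reader might infer that the table cannot show an acute QT effect at all. The documents do not support that. Visit 1 post-dose changes already use the same-day pre-dose ECG, and three of the five categories need no baseline. Under Illustration A false entries above 60 msec are rare even at Visit 3.

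A reader might also take the Visit 3 baseline as an error or a departure from the protocol. It is neither. Protocol 7.5.5 says only baseline, and the Treatment Period 2 baseline is a valid reference for total on-treatment change, including any persistent effect that a same-day baseline would subtract.

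Nor does SAP 3.5's mention of descriptive statistics contradict a category table: SAP 9.4 lists counts and percentages as summaries for discrete variables.

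All QTc values will be listed by subject, so same-day changes can be derived. That is true, but SAP 15.8 specifies listing the intervals and the overall result, not changes, so each reader would have to compute them.

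Finally, the SDs and the 10 subjects are assumptions. This stands in full.

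**Conclusion.** The point holds in limited form. The >30 to 60 and >60 msec categories at Visit 3 do not separate an acute post-dose effect from 50 to 62 days of drift and cumulative exposure, although the ECG needed to do so is collected. The table also lacks the central-tendency summary that the protocol planned at Visits 1 and 3, an omission disclosed only through the general early-closure statement. With at most 25 subjects, it is insensitive to a moderate mean shift.

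The baseline rule and the omission follow from the text. The size does not: 7.1% against 0.4%, and 14.6 against 8.1 msec, depend on the assumed SDs and on n = 10, and the baseline gain disappears if between-visit variance and drift are negligible. This is a worthwhile, inexpensive addition, not a defect that invalidates the table.

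**What to change.** Keep the five categories and the Treatment Period 2 baseline in Table 14.3.3.7, described as total on-treatment change. Add:

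- for Visit 3 at 15, 60, 120 and 360 minutes, change in QTcF and QTcB from the Visit 3 same-day pre-dose ECG;
- for Visits 1 and 3, n, mean, SD and 95% CI of change at each post-dose time point;
- a statement of whether the categories count each time point or each subject's worst value, which SAP 15.8 leaves open;
- a line in SAP section 20 naming any part of the Protocol 7.5.5 QTc analysis that is still omitted.

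The cost is one more panel in a table already being programmed, with no new data. The same-day change has limits. There is no placebo day, so diurnal variation remains. It also cannot separate Sodium Cridanimod from the megestrol and lidocaine given at the same visit. It should therefore supplement the Treatment Period 2 baseline, not replace it.

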15.9 Routine Clinical Laboratory Data

15.9.1 HEMATOLOGY

Blood samples (5 mL) will be taken at the Screening Visit, at each Study Visit, at the End of Study-TP1Visit, and at the Safety Follow-UpTP2 Visit and used for routine hematology analysis at local laboratories.

Hematology profile will include:

- Differential Leukocyte Count (Basophils, Eosinophils, Lymphocytes, Monocytes, and Neutrophils) (cells $\times 10^9/L$)
- Erythrocytes (cells $\times 10^{12}/L$)
- Hematocrit (L/L)
- Hemoglobin (g/L)
- Leukocytes (cells $\times 10^9/L$)
- Mean Corpuscular Hemoglobin Concentration (MCHC) (mmol/L)
- Mean Corpuscular Volume (MCV) (μm^3)
- Platelets (cells $\times 10^9/L$)

15.9.2 SERUM CHEMISTRY

Blood samples (5 mL) will be taken at the Screening Visit, at each Study Visit, at the End of Study-TP1 Visit, and at the Safety Follow-Up TP2 Visit and used for routine serum chemistry analysis at local laboratories.

Chemistry profile will include:

- Albumin (g/L)
- Alkaline Phosphatase (μkat/L)
- Alanine Aminotransferase (ALT)/Serum Glutamic Pyruvic Transaminase (SGPT) (U/L)
- Aspartate Aminotransferase (AST)/Serum Glutamic Oxaloacetic Transaminase (SGOT) (U/L)
- Bicarbonate (mmol/L)
- Blood Urea Nitrogen (BUN) (mmol/L)
- Calcium (mmol/L)
- Chloride (mmol/L)
- Creatine Kinase (nkat/L)
- Creatinine (μmol/L)
- Glucose (mmol/L)
- Lactate Dehydrogenase (LDH) (μkat/L)
- Phosphate (mmol/L)
- Potassium (mmol/L)
- Sodium (mmol/L)
- Total Bilirubin (μmol/L)
- Total Protein (g/L)

Estimated Glomerular Filtration Rate (eGFR, mL/min/1.73 m²) will be calculated based on blood creatinine levels and subject demographics using the CKD Epidemiology Collaboration (CKD-EPI) method:

$$GFR = 141 \times \min(\text{Scr}/\kappa, 1)^\alpha \times \max(\text{Scr}/\kappa, 1) - 1.209 \times 0.993 \text{Age} \times 1.018 \text{ [if female]} \times 1.159 \text{ [if black]}$$

where:

Scr is serum creatinine in mg/dL,
 κ is 0.7 for females and 0.9 for males,
 α is -0.329 for females and -0.411 for males,
min indicates the minimum of Scr/k or 1, and
max indicates the maximum of Scr/k or 1

(<https://www.niddk.nih.gov/health-information/communication-programs/nkdep/laboratory-evaluation/glomerular-filtration-rate-calculators/ckd-epi-adults-conventional-units>).

This formula incorporates normalization to 1.73 m² body surface area, which is an accepted average adult surface area. Results are reported in mL/min/1.73 m².

15.9.3 URINALYSIS

Urine samples are taken at the Screening Visit, at the End of Study Visit, at Visit 7, at Visit 13, every 12 weeks thereafter until disease progression and at the Safety Follow-Up Visit, and are analyzed at local laboratories.

Urine analysis will include:

- Blood
- Glucose
- Ketones
- pH
- Protein

The local laboratories will provide lab results, normal ranges and units to be entered on the eCRFs. All laboratory data will be converted to standard international units for reporting purposes.

Routine clinical laboratory evaluations (hematology, serum chemistry, and urinalysis) will be listed by subject with values outside of reference ranges marked. The high/low criteria will be determined based on the normal ranges provided by the laboratory.

16. Pharmacokinetic (PK) Analyses

No patients participated in the voluntary PK portion of the study therefore no PK data will be presented in the abbreviated analysis.

17. Pharmacodynamic Analyses

No Pharmacodynamic data will be collected for this study.

18. Quality of Life Analyses

No Quality of Life data will be collected for this study.

19. Interim Analyses

Since the study is closing early no interim analysis will be performed.

20. Changes from Protocol-Stated Analyses

Since the study is closing early, this SAP differs from the protocol-stated analysis in significant respects.

With the exception of one ECG table (summarizing QTc categories) all data will only be presented in listings. Two other particular differences are noted:

1. Protocol 7.2.1 states, "The Safety Population will consist of all subjects who receive at least one full or partial dose of study treatment (all treated subjects) in Treatment Period 2. This population will be used for all safety reporting." This SAP updates this to the following definition: The Safety Population will consist of all subjects who receive at least one full or partial dose of either study treatment. For subjects treated solely in Treatment Period 1 this will include all subjects treated with at least one full or partial dose of MA. For all other subjects, the Safety Population will include all subjects treated with at least one full or partial dose of either MA or SC. Safety data will be reported separately for subjects in Treatment Period 1 who do not go on to Treatment Period 2, and for those subjects in Treatment Period 1 who are treated in both periods.
2. The primary efficacy endpoint ODCR and secondary efficacy endpoint ORR will not be assessed.
3. Protocol 7.7 indicates that protocol deviations will be collected on the eCRFs. Instead, deviations will be collected and monitored by the site monitors and transferred to SDC as an Excel spreadsheet.

Any changes to the planned analyses after database lock and unblinding will be described in the clinical study report.

21. References

R. P. A'Hern. Sample size tables for exact single-stage phase II designs. *Statist. Med.* 2001; 20:859:866.

Fleming TR. One sample multiple testing procedure for phase II clinical trials. *Biometrics* 1982; 38:143:151.

22. Revision History

Documentation of revision to the SAP will commence after approval of the Final version 1.0.

23. Tables

14.3.3.7	Electrocardiogram QTcB and QTcF Categories	Safety Population
----------	--	-------------------

24. Figures

14.2.1.1	Swimmer's Plot of Treatment and Response Durations	Safety Population Population – Subjects who Participated in Treatment Period 2
----------	--	---

25. Listings

Listing Number	Title	Population
16.2.1.1	Subject Disposition	All Enrolled Subjects
16.2.1.2	Screen Failures	All Screened Subjects
16.2.1.3	Informed Consent	All Enrolled Subjects
16.2.1.4	Visit Dates	All Enrolled Subjects
16.2.1.5	Inclusion and Exclusion	All Enrolled Subjects
16.2.2	Protocol Deviations	All Enrolled Subjects
16.2.3	Analysis and Treatment Period Populations	All Enrolled Subjects
16.2.4.1	Demographics and Baseline Characteristics	Safety Population
16.2.4.2	Baseline Disease Characteristics and PrR Status	Safety Population
16.2.4.3	Medical and Surgical History	Safety Population
16.2.4.4	Prior and Concomitant Medications	Safety Population
16.2.4.5.1	Prior Chemotherapy	Safety Population
16.2.4.5.2	Prior Hormonal Therapy	Safety Population
16.2.4.5.3	Prior Radiotherapy	Safety Population
16.2.4.5.4	Prior Cancer Surgery	Safety Population
16.2.4.6	Pregnancy Test Results	Safety Population
16.2.5.1	Sodium Cridanimod Administration	Safety Population

Listing Number	Title	Population
16.2.5.2	Megestrol Acetate Diary	Safety Population
16.2.5.3	Megestrol Acetate Accountability	Safety Population
16.2.6.1	Investigator Target Lesion Assessments by Visit	Full Analysis Set
16.2.6.2	Summary of Investigator Target Lesion Assessments and New Lesions by Visit	Full Analysis Set
16.2.6.3	Investigator Non-Target Lesion Assessments by Visit	Full Analysis Set
16.2.6.4	Best Overall Response	Full Analysis Set
16.2.6.5	Duration of Stable Disease Events	Full Analysis Set – Treatment Period 2 only
16.2.6.6	Progression-Free Survival Events	Full Analysis Set – Treatment Period 2 only
16.2.6.7	Overall Survival Events	Full Analysis Set – Treatment Period 2 only
16.2.7.1	Adverse Events	Safety Population
16.2.7.2	Serious Adverse Events	Safety Population
16.2.7.3	Treatment-Emergent Adverse Events Leading to Discontinuation from Treatment Period 1	Safety Population
16.2.7.4	Treatment-Emergent Adverse Events Leading to Discontinuation from Treatment Period 2	Safety Population
16.2.7.5	Treatment-Emergent Adverse Events as Reason for Not Completing Safety Follow-Up	Safety Population
16.2.7.6	Treatment-Emergent Adverse Events with Outcome of Death	Safety Population
16.2.7.7	Mortality	Safety Population
16.2.8.1	Physical Exam Results	Safety Population
16.2.8.2	Vital Signs Results	Safety Population
16.2.8.3	Height, Weight, and BMI Results	Safety Population
16.2.8.4	GOG Performance Status	Safety Population
16.2.8.5	Electrocardiogram Results	Safety Population
16.2.8.6	Hematology Laboratory Results	Safety Population
16.2.8.7	Serum Chemistry Laboratory Results	Safety Population
16.2.8.8	Urinalysis Laboratory Results	Safety Population
